## PROTOCOL SYNOPSIS

Protocol Title	Escape Room: A gamified approach to learning about cancer nutrition information
Protocol Number	
Protocol Sponsor	Fred Hutchinson Cancer Center
Trial Phase	Early Phase/Phase 1
Trial Type	Single arm, open trial
	Aim 1 To evaluate the feasibility, acceptability, and usability of the escape room game intervention among breast cancer patients in active treatment.
Study Objectives	Exploratory Aim 2 To test preliminary efficacy of the escape room game intervention for increasing awareness about types of online misinformation, concern about misinformation, and confidence in the ability to identify misinformation as well as decreasing cancer nutrition misinformation beliefs.
Study Design	Feasibility study (Aims 1 and 2)
Population	Patients with a current diagnosis of breast cancer (Stages I-III) and in active treatment for breast cancer.
Primary Endpoints	Study design and intervention feasibility, acceptability, usability, and potential efficacy of an escape room game will be measured by assessing accrual rate, satisfaction, and usability of the escape room game.
Secondary Endpoints	Awareness and concern about cancer nutrition misinformation and beliefs about cancer nutrition.
Type of Control	N/A (single arm, open trial)
Treatment Group	Escape room game
Treatment Schedule	Intervention (Escape Room Game): 
 
- Pre-game baseline survey
 
- Play the misinformation escape room game intervention in groups of approximately 5 and completed debrief exit interview
 
- Post-game survey
 

Number of participants	N=40 (n=5 breast cancer patients per group)
Estimated duration of study (per participant)	4 weeks
Duration of participation (per participant)	90 minutes

## ABBREVIATIONS

*Include a table of abbreviations as needed.*

EHR	Electronic health record
Fred Hutch	Fred Hutchinson Cancer Center
UW	University of Washington

## 2.0 INTRODUCTION TO THE PROTOCOL

### 2.1 Introduction

The described study will be conducted in compliance with all applicable IRB requirements and associated Federal regulations.

The overarching goal of this research study is to pilot test an escape room intervention for cancer nutrition misinformation designed to reduce vulnerability to believing cancer nutrition misinformation among breast cancer patients. The results of this pilot study will provide necessary preliminary data to apply for an NIH R01 level application to conduct a full randomized controlled trial (RCT) of the escape room game as a potential intervention to increase resistance to cancer nutrition misinformation.

[name] (Co-I) and [name] (Co-I) at the University of Washington (UW), along with collaborator [name] (Puzzle Break), previously developed an online misinformation escape room as an interactive learning experience designed to focus on the psychological dimensions of misinformation. Escape rooms are live action-adventure games where teams work cooperatively to solve a series of puzzles. Initial results were encouraging, indicating the game successfully increased awareness of misinformation and confidence in identifying it. Based on this experience, the UW research team and [name] (PI) at Fred Hutch partnered to develop an escape room for cancer nutrition misinformation. This project builds off [name] key strengths as a cancer communication researcher and builds on a novel and relevant area of public health – combating cancer misinformation. Expertise from oncologists and cancer nutrition experts about the types of misinformation they encounter in their work with patients was also incorporated into developing the escape room content.

### 2.2 Background

The COVID-19 pandemic has brought to the forefront both the prevalence and dangers of health misinformation among the U.S. population. Misinformation, or communication about health information that is inaccurate or false, has serious health consequences for those that believe it. The rise of the access to and use of the various sources of information on the internet such as websites and social media has caused the spread of misinformation and disinformation to grow rapidly, creating far-reaching negative consequences on health outcomes. Cancer misinformation, in particular, has become an increasingly prevalent issue that poses a real public health threat to the many cancer patients in the U.S. One area of this landscape is cancer nutrition misinformation, which can propel patients into engaging in health behaviors that may negatively affect their treatment and survival outcomes or avoiding positive health behaviors that may benefit them.

Misinformation around nutrition is prevalent. One study found that health claims such as prevent (41.8%), treat (27.2%), and cure (10.7%) cancer and phrases such as “anti-cancer” or “cancer-fighting” were common among recipes posted to the website Pinterest. Prior research indicates that core components of information seeking such as trustworthiness are critical to determining peoples’ likelihood of believing and acting upon misinformation. However, in the context of online information where misinformation thrives, it can be very difficult to determine whether a source is truly trustworthy or accurate. Thus, in turn, makes patients highly vulnerable to cancer nutrition misinformation through online routes of obtaining information. Because proper nutrition is critical to patients being able to receive proper cancer treatment and manage symptoms associated with treatment, it is critical that patients receive access to accurate cancer nutrition information.

Unfortunately, education alone is rarely an effective form of intervention for combating misinformation. This project will build on prior stages of research aiming to develop a gamified approach to building resilience to public health misinformation, with a specific focus on cancer nutrition misinformation. *Gamification* is a promising new target for combating misinformation, as it provides a way to help users learn new skills (such as developing awareness of and resistance to misinformation) through the psychologically non-threatening form of play. This approach involves the creation of an escape room game that will help people detect and resist misinformation through an immersive learning experience which focuses on cognitive biases, emotional triggers, and other affective attributes of misinformation.

## 2.3 Risks/Benefits

### Risks

- Discomfort. There may be some emotional discomfort in discussing misinformation and disinformation rhetoric in relation to health and nutrition related topics. We do not anticipate that this discomfort will be exacerbated by a group setting. Indeed, misinformation researchers use group reflection meetings to mitigate the emotional impact of being exposed to misleading and problematic information. The UW's Center for an Informed Public builds group reflection meetings into research timelines for their student researchers as group reflection on misleading information has allowed researchers to maintain clarity in confusing information environments and provided them with a supportive space to share any concerns around the information they encounter. We anticipate that this same framework will apply to the cancer patient population. Further, the Misinformation Escape Room has been designed using expert insight from in-depth interviews with oncologists and cancer nutrition experts and will be, prior to player testing, evaluated by the same experts to ensure it is appropriate for this specific patient population. Finally, we have proper oversight and monitoring of any adverse events created by participating in group settings in order to ensure an accurate oversight of and response to any potential distress is part of the research plan. Participants can decline to complete the intervention, survey or interview or skip questions at their own discretion.
- Loss of privacy. A risk of taking part in this study is the possibility of a loss of confidentiality. Loss of confidentiality includes having your personal information shared with someone who is not on the study team and was not supposed to see or know about your information. We will try to protect your information, but we cannot guarantee privacy. The plans for keeping your information private are described in the 'confidentiality' section of this consent form.

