**Table 1. Survey measures to be collected**

	Screening	Baseline	Post -completion of intervention (+ 1 week)
Demographics & clinical characteristics	X	X	
Disease status and treatment		X	X
Behaviors done based on information consumed online (a 6-item background checklist such as "taken over-the-counter medicine")		X	
Aim 1			
Feasibility			X
Acceptability			X
Usability			X
Aim 2			
Types of online information (as measured by 6-item checklist about sources of nutrition information utilized)		X	
Concern about misinformation and confidence in identifying misinformation			X
Cancer nutrition misinformation beliefs (as measured by cancer nutrition beliefs)		X	X
Additional exploratory variables			
Trust and information-seeking		X	X
Vulnerability to misinformation		X	X
Healthy skepticism		X	X
Confidence in and motivation to share information with a medical professional		X	X
Awareness of misinformation		X	X
Exit/debrief questions and interview			
Game enjoyment/recommendation to others			X
Qualitative exit interview			X

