## Data Collection

Eligible participants will undergo in person or remote assessments that will include in person, over the phone, video conferencing, and/or web-based data collection.

Data collection will include completion of a written or electronic eConsent form via a secure HIPPA-compliant REDCap survey and the following assessments: (1) Questionnaires assessing demographics, medical history, clinical characteristics (pre- and post-intervention); (2) *Feasibility* will be assessed by rates of accrual to the study; (3) *Acceptability* will be assessed using two Likert-type scales to assess satisfaction (1 = not at all satisfied, 10 = very satisfied) and likelihood to recommend the game to someone else (1 = not at all likely, 5 = very likely) (post-intervention); (4) *Usability* will be assessed with the System Usability Scale (SUS) (post-intervention only), which is a 10-item scale, scored on a 5-point Likert scale (1 = strongly disagree, 5 = strongly agree) (post-intervention); (5) *sources of nutrition information utilized* (6-item checklist) (baseline), (6) *behaviors done based on information consumed online* (6-item checklist) (baseline); (7) *trust and information-seeking* (5-item scale scored on a 7-point Likert scale; 1 = strongly disagree, 7 = strongly agree) (baseline and post-intervention); (8) *vulnerability to misinformation* (3-item scale scored on a 7-point Likert scale; 1 = strongly disagree, 7 = strongly agree) (baseline and post-intervention); (9) *healthy skepticism* (6-item scale scored on a 7-point Likert scale; 1 = strongly disagree, 7 = strongly agree) (baseline and post-intervention); (10) *confidence in sharing and motivation to share information with a medical professional* (2 items from the "Confidence Sharing Information with a Medical Professional" scale scored on a 7-point Likert scale; 1 = not at all confident; 7 = very confident and 2 adapted items to measure degree of motivation; 1 = not at all motivated, 7 = very motivated) (baseline and post-intervention); (11) *Awareness of misinformation* (baseline and post-intervention), (12) *Concern about misinformation and confidence in identifying misinformation* (baseline and post-intervention), (13) *Cancer nutrition information beliefs* (baseline and post-intervention), and (14) brief semi-structured feedback exit interview (post-intervention only).

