  - *Trust and information-seeking* will be assessed using a validated 5-item measure asking the degree to which individuals trust health information sources (e.g., “I trust the health information I get from my doctor”). This scale is rated on a 7-point Likert scale indicating the degree to which individuals agree with each statement (1 = strongly disagree, 7 = strongly agree).
  - *Vulnerability to misinformation* will be assessed using a validated 3-item measure that asks participants the degree to which they believe they or those in their social network are vulnerable to misinformation (e.g., “I am able to identify news or information that misrepresent reality or is even false.” Items are rated on a 7-point Likert scale (1 = strongly disagree, 7 = strongly agree).
  - *Healthy skepticism* will be assessed using an adapted version of a validated 6-item measure that measures the degree to which participants are skeptical of online posts (e.g., “I am confident in my assessment of this post as emotionally manipulative/overgeneralizes/doesn’t refer to authoritative evidence/cherry picks data”). Items are rated on a 7-point Likert scale (1 = strongly disagree, 7 = strongly agree).
  - *Confidence in sharing information with a medical professional* will be assessed using three adapted items from the validated “Confidence Sharing Information with a Medical Professional” scale. Items ask participants the degree to which they are confident or motivated in sharing information with their doctor (e.g., “How confident are you in your ability to ask a doctor for more information if you don’t understand what he or she said?”). Items are rated on a 7-point Likert scale (1 = not at all confident, 7 = very confident).
  - *Awareness of misinformation* will be measured using our 5-item scale used in our prior study to assess the degree to which the intervention makes users more aware of misinformation types and common tactics (e.g., emotionally charged language, false data; 1 = not at all aware, 7 = fully aware).
- **Exit/debrief questions and interview:**
  - *Game enjoyment/recommendation to others* will be measured using an adapted version of a 12-item scale designed to assess how much individuals enjoyed the game and would recommend it to others (e.g., “I felt content”). Items are rated on a 5-point Likert scale (0 = not at all, 4 = extremely).

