## 7.2 Semi-structured Qualitative Interview

A brief semi-structured feedback interview will be conducted to gain additional insights and feedback for modifications needed to the intervention to optimize it. Immediately after the escape room session, a nutrition expert will facilitate a 15-20 minute group interview with the participants to give them an opportunity to reflect on their experience with the game. The objective of the semi-structured group interview is to understand how participants’ attitudes and feelings about misinformation may have been impacted by the escape room experience. The interview will also explore how vulnerable participants feel to health information and their comfort level with questioning the source and nature of information. The nutrition expert will use a short

interview guide (9 questions) to facilitate the group interview. The role of the facilitator will be to elicit people's opinions and allow others to carry the conversation, making sure the discussion stays on topic and stepping in to provide additional information as a nutritional expert.

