### 10.2 Adverse Event Grading Scale

**0 = No Adverse Event** or within normal limits.

**1 = Mild Severity:** Transient laboratory test alterations; discomforts noted but no disruption of daily activities; no therapy, or only symptomatic therapy required.

**2 = Moderate Severity:** Laboratory test alterations indicating injury without long-term risk; discomfort sufficient to modify normal daily activity; specific therapy required (i.e., more than symptomatic).

**3 = Serious Severity:** Laboratory test indicating a serious health threat or permanent injury; incapacity, inability to work, inability to perform normal daily activity; hospitalization required or prolonged; emergency treatment required; life-threatening events; death.

**Plan for unanticipated AE reporting:** All unanticipated AEs related to the study procedures that are severe or serious will be reported by [name] to the IRB within 10 days of notification of the investigator.

**Plan for anticipated AE reporting:** All anticipated AEs related to the study procedures will be documented in the study's Reportable Events Log.

**Plan for ongoing review of results:** The PI will be notified within 24 hours by the research manager of any early terminations due to an adverse event.

**Plan for safety review:** The PI will perform a cumulative review of all adverse events and premature terminations review every 3 months after study initiation or after completion of 50% of participant visits, whichever occurs first.

**Plan for annual reporting:** A summary of the investigation including all adverse events and how they were handled, enrollment, drop-outs and reason for discontinuation and any protocol modifications will be provided to the IRB on an annual basis.

Annual Reports will contain:

- a. The number of adverse events and an explanation of how each event was handled.
- b. The number of complaints and how each complaint was handled.
- c. The number of participant withdrawals and an explanation of why the participant withdrew or was withdrawn.
- d. The number of protocol deviations and how each was handled.

The occurrence of any serious and unexpected event may prompt changes in study protocol. Any such change will be approved by the IRB before implementation.

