**Table 2. Data monitoring**

Activity	Report	Timing of review by PI
Study Recruitment	Weekly report generated by CRC	Weekly PI review
Enrollment	Weekly report generated by CRC	Weekly PI review
Study Retention	Weekly report generated by CRC	Weekly PI review
Informed Consent	Quality control of each new consent	PI reviews all consents upon receipt
Interviews/Self-Report Measures	PI and other study staff will review all interview and self-report materials and complete fidelity checklist	PI will review data weekly for completeness and accurate entry into a spreadsheet for analysis

A data safety and monitoring committee is not needed as this is not a Phase 3 clinical trial. [name] (PI) will oversee the data safety and monitoring for this project. She will meet with the study staff to discuss protocols and procedures to ensure participant safety and the validity and integrity of the study data. All staff

members will attend trainings on these procedures and will be given information on the importance of reporting any adverse event immediately. [name] and the IRB will be alerted about any adverse events immediately. [name] will discuss any adverse effects and examine available data to assess whether safety is compromised. Action to resolve the adverse event will be discussed with IRB prior to implementation. The team will enact any actions recommended by the IRB.

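### Section 2.3 says distress from group play is monitored, but no listed measure, Table 1 row or Table 2 activity asks about it, so a low count could not be read as absence of distress

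*Combined protocol and SAP*

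**What the plan says.** Section 2.3 opens its list of risks with "There may be some emotional discomfort in discussing misinformation and disinformation rhetoric in relation to health and nutrition related topics". It expects no worsening from the group setting, an expectation carried over from experience with student researchers. It then states that "we have proper oversight and monitoring of any adverse events created by participating in group settings" and presents this as the means by which distress will be seen and answered.

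After the game, the plan collects the following:

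- Table 1 schedules feasibility, acceptability, usability, the misinformation scales, "Game enjoyment/recommendation to others" and the exit interview. Section 7.1 describes the enjoyment scale as "designed to assess how much individuals enjoyed the game and would recommend it to others".
- Section 7.2 provides a debrief: "Immediately after the escape room session, a nutrition expert will facilitate a 15-20 minute group interview with the participants". Its stated aims are attitudes and feelings about misinformation, perceived vulnerability, and comfort with questioning sources.

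On safety, section 10.1 has adverse events entered on an Adverse Event Summary Form. Section 10.2 grades them, and grade 1 includes "discomforts noted but no disruption of daily activities". It also provides for prompt notice to the PI of early terminations due to an adverse event, a periodic cumulative PI review, and an annual report that counts adverse events, complaints and withdrawals. Table 2 in section 11.0 lists five monitoring activities. For interviews and self-report measures, the timing column reads "PI will review data weekly for completeness and accurate entry into a spreadsheet for analysis".

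**The concern.** The plan makes a specific statement that distress is monitored, and mild discomfort is a gradable event under its own scale. Mild discomfort is also the kind of event a patient is least likely to raise unprompted, particularly on a video call in front of other players. If nobody is asked, the recorded count mixes two things that cannot be separated afterwards: how often distress occurred, and how often it came to someone's attention.

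The pilot is meant to supply preliminary data for a full randomised trial, and the absolute frequency of distress is useful information for that step. A reported figure of zero or one, gathered passively, would look reassuring without being informative. For the patients themselves, distress that nobody notices cannot be responded to.

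**Working it through.** No figure in the plan bears on this point, so there is none to reproduce. The first step is to look for a procedure; the second is an illustration of what passive capture does to the count.

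**Step 1. Is there a procedure that asks about distress?**

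- Section 6.3, Data Collection: 14 items, none on distress, mood or adverse events.
- Table 1: no such row. The nearest are game enjoyment and the exit interview.
- Section 7.1: no such scale is described. The nearest is the adapted 12-item enjoyment scale, of which one positively worded item is shown.
- Section 7.2: the debrief touches on feelings, but about misinformation, in the group, and with no stated link to the adverse event form.
- Sections 10.1 and 10.2: form, grades, reviews and reports are given. No question, time point or observation window for finding an event is given.
- Table 2: recruitment, enrollment, retention, consent, and interviews/self-report measures. None is for adverse events, and the stated purpose of the PI's weekly review of self-report data is completeness and correct entry.

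The remaining routes into the record are spontaneous report, staff observation and reasons for withdrawal.

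**Step 2. What passive capture does to the count (illustration only).**

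Inputs: N = 40 (section 6.2; 8 groups × 5 = 40). The true distress rate p and the captured fraction s are not in the documents. I assume p = 5%, 10% or 20% and s = 25%, 50% or 100%, with patients independent.

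Expected number recorded = 40 × p × s. At p = 10% there are 40 × 0.10 = 4 true cases, of which 1, 2 or 4 are recorded at s = 25%, 50% or 100%.

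Chance of recording none = (1 − p × s)^40:

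| True rate p | s = 25% | s = 50% | s = 100% |
|---|---|---|---|
| 5% | 0.9875^40 = 60% | 0.975^40 = 36% | 0.95^40 = 13% |
| 10% | 0.975^40 = 36% | 0.95^40 = 13% | 0.90^40 = 1.5% |
| 20% | 0.95^40 = 13% | 0.90^40 = 1.5% | 0.80^40 < 0.1% |

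Read the other way, if no case is recorded in 40 patients, the one-sided 95% upper limit for the recorded rate is 1 − 0.05^(1/40) = 7.2%. That is a limit on the true rate only if every case is captured. Otherwise it must be divided by s: 7.2% / 0.50 = 14.4% at half capture, and 28.9% at a quarter (0.07216 / 0.25).

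Independence is a simplification, because patients play in groups of about 5. Positive correlation within groups would raise the chance of recording none at every rate.

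**The case against.** The strongest reply is that the plan has more safety machinery than its tables suggest. Section 11.0 has staff trained to report any adverse event at once. A member of the research team is present at every debrief (sections 3.4 and 7.2). Early terminations due to an adverse event reach the PI, and withdrawals must be explained in the annual report (section 10.2). The study is described as low-risk.

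All of this stands, and it rules out several stronger readings that a reader might infer:

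- *That only complaints volunteered by patients would be counted.* Staff-observed events and explained withdrawals can also enter the record.
- *That no monitoring report covers adverse events.* Table 2 has no such line, but section 10.2 has the cumulative review and the annual report. These summarise what was recorded; they do not elicit it.
- *That the section 10.2 grades cannot be applied.* The fields of the Adverse Event Summary Form are not shown, and staff could ask about daily activities when completing it. The gap is in finding events.
- *That few or no events would be reported whatever the true rate.* The table above does not support this: at a 10% rate and quarter capture, at least one case is still recorded with probability 64% (1 − 0.36).
- *That the study fails to test whether the group setting adds distress.* Section 2.3 states an expectation, not a hypothesis. Every patient plays in a group, so this single-arm study could not test it with or without a distress item.

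The 9-question debrief guide and most of the enjoyment items are also not shown, so a relevant question there cannot be excluded. Even so, a group discussion with no stated link to the adverse event form is not individual, private ascertainment, and the other routes all depend on someone speaking up or noticing.

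**Conclusion.** The point holds as a gap in ascertainment. The plan says distress from group participation is monitored, but no listed measure, Table 1 row or Table 2 activity actively asks about it, and no section says how events are to be found. A low or zero count under this plan could not be read as absence of distress.

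Its size depends on two quantities the documents do not give. Over assumed rates of 5% to 20%, quarter capture leaves a 60% to 13% chance of recording no case, against 13% to under 0.1% with full capture. These figures show direction and rough scale; they are not a forecast. The conclusion that capture is passive does not depend on them, though it rests on the measures as described, since the debrief guide and the full enjoyment scale are not shown. In a low-risk pilot this is a modest but worthwhile improvement, and it does not undermine the Aim 1 or Aim 2 analyses.

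**What to change.** Add two privately answered items to the existing post-game survey:

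1. How upsetting the game or the group discussion was, rated 0 to 10.
2. Whether any upset disrupted daily activities.

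Put the same two items to anyone who leaves early. Add matching rows to Table 1 and to Table 2, the latter under the weekly PI review that already exists. State that positive answers, and any distress disclosed in the debrief, are entered on the Adverse Event Summary Form and graded by staff under section 10.2. Report the distribution of the two items descriptively alongside the Aim 1 results.

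Two limits should be stated. The items alone do not yield a section 10.2 grade, which also turns on therapy required and hospitalisation. Nor do they test whether the group setting adds distress; they give an absolute frequency.

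The cost is two survey items, one row in each table and a minor amendment, with no new visit and no change in sample size. The downside is a slightly longer survey and probably more mild events reported. Full capture also assumes that patients answer the items, so the number who did should be reported with the results.
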